4.5 Study Data Collection Timing and Methods

The expected duration of the study is maximum of 36 months. The expected duration of recruitment is 18 months. Participants will be followed-up for up to 18 months of cabozantinib treatment. If cabozantinib is discontinued during the first 15 months of observation, and a subsequent therapy is started, a follow-up visit will be performed approximately 3 months after discontinuation of cabozantinib. Enrolment in the study is possible if cabozantinib treatment started up to 4 weeks prior to enrolment. The data for Visit 1 will be captured retrospectively. Starting at Visit 2 data will be collected prospectively including hrQoL baseline assessment. Patients who have started cabozantinib treatment up to 4 weeks before giving informed consent but stopped treatment during the 4 weeks may be included.

Three visit types will be performed:

- Baseline Inclusion/ Treatment Initiation Visit (Visit 1)
- Regular visit during the observational period (Visits 2 to 9) approximately every month until Month 3 and every 3 months afterwards
- Follow-up visit for participants discontinuing cabozantinib treatment during the 15-month observational period

All data will be recorded as applicable and available during standard of care routine. If a specific diagnostic procedure or assessment is done according to clinical routine the corresponding data should be recorded in the eCRF, otherwise the corresponding part of the eCRF will be marked as not done / not available.

The timing of the visits according to routine clinical practice is assumed to be close to the proposed schedule. If the timing does not meet the schedule, entries should be made at the visit nearest in time to the proposed schedule.

For regular visits during the observation period the minimum information that must be recorded is the most recent result of the tumour assessment at/before Visit 1 to obtain a baseline value required for determination of the primary endpoint, DCR. Minimum required information for follow up visits after therapy switch, i.e. starting a new LoT includes the start date of new treatment (partial dates are allowed) and the type of treatment.

Adverse events (including treatment-emergent nonserious AEs and serious adverse events (SAEs)) and Special Situations (SS) including pregnancy will be collected during the observation period, see Section 9.

Inclusion/Treatment Initiation (Visit 1)

The following data will be collected:

- Date of signed informed consent.
- Date of visit.
- Eligibility (verification of the inclusion and exclusion criteria, see Section 5.1 and Section 5.2.
- Demographic and baseline characteristics:
 - Year of birth and gender.

PAGE 24/52

PROTOCOL FINAL V1.0: 30 JULY 2025

- Baseline clinical characteristics:
 - Height (centimetres), Weight (kilograms).
 - Systolic and diastolic blood pressure (mmHg).
 - Heart frequency (bpm).
- Significant medical and surgical history.
- NET diagnosis:
 - Date of initial diagnosis.
 - Primary tumour location.
 - Grade (at first diagnosis and at baseline).
 - Stage (at first diagnosis and at baseline).
 - Ki67 Index (at first diagnosis and at baseline).
 - Hormone secretion.
- Prior systemic NET therapies. For each LoT:
 - Drug name.
 - Start and stop date.
 - Reason for discontinuation.
 - LoT.
- Prior NET related radiotherapies:
 - Start and Stop date.
 - Duration.
- Prior NET related surgeries:
 - Location.
 - Date.
- Baseline tumour assessment:
 - Date of last imaging (reference images).
 - Type.
- Eastern Cooperative Oncology Group (ECOG) performance status:
- Cabozantinib regimen:
 - Start date.
 - Dose.
- NET biochemical markers:
 - Chromogranin A (CgA).
 - Neuron-specific Enolase (NSE).
- EORTC QLQ-C30 and QLQ-GINET21 questionnaire every 3 months until the last visit while taking cabozantinib.
- Supporting measures:
 - participation in a patient support program (PSP).
 - psycho-oncological support.
 - special skin care.
 - special mouth care.

- nutritional advice.
- nutritional substitution.
 - high calorie drinks.
 - parenteral nutrition.
- Vitamin substitution for NET, NET-therapy or symptoms:
 - Vitamin C.
 - Lipid soluble vitamins.
 - Combination vitamins.
 - Other.
- Concomitant NET medication (including concomitant medications for AEs).
- All AEs and SS will be collected from the first intake of cabozantinib.

Treatment Period visits (Visit 2 to Visit 9)

As this is a non-interventional study, no formal schedule for Treatment Period visits could be planned. During the Treatment Period, data of interest will be collected at visits occurring as per routine/ standard clinical practice approximately every month until Month 3, and then approximately every 3 months onwards. If two visits or more occur within a 3-month window, only the visit closest to the time point should be reported with most relevant information.

The following data will be collected:

- Date of visit.
- Tumour assessment (TA):
 - by the investigator (clinical and radiographic). If radiological assessment is performed, it should be indicated whether the assessment of progression is based on Response Evaluation Criteria in Solid Tumours 1.1 guidelines (RECIST 1.1) or local standard of care. The most recent radiographic assessment performed before the visit is to be reported with the date and overall response. If clinical assessment is performed, the date of progression is to be provided if applicable. An assessment via imaging is expected approximately every 3 months as per standard of care.
- ECOG performance status.
- Cabozantinib regimen:
 - (Start date, stop date, administered dose, frequency, primary reason for dose change or discontinuation).
- Clinical characteristics:
 - weight, systolic and diastolic blood pressure; heart frequency.
- NET biochemical markers:
 - CgA.
 - NSE.
- EORTC QLQ-C30 and QLQ-GINET21 questionnaire every 3 months until the last visit while taking cabozantinib.
- Supporting measures (see Visit 1).
- Concomitant NET medication (including concomitant medications for AEs).
- Concomitant non-drug NET therapy.
- Adverse Events and Special Situations:

PAGE 26/52

- From Visit 1 onwards until the End of Study (EoS), treatment-emergent nonserious AEs and SAEs and SS including pregnancy occurring during the data reporting period at each visit will be reported. Any clinically significant (CS) findings (as assessed by the investigator) on physical examination, laboratory values and electrocardiograms (ECGs) performed as per routine/ standard clinical practice will be reported as AEs.

If a participant withdraws consent, data will be collected up to the time of withdrawal, with no additional information collected thereafter.

Post-cabozantinib Treatment Follow-up Period:

For participants who discontinued cabozantinib during the first 15 months of observation, a follow-up visit at approximately 3 months after discontinuation should be documented, as the next standard of care visit for the next LoT is expected.

The following data will be collected:

- Date of visit/contact.
- ECOG Performance Status.
- Subsequent treatment following cabozantinib discontinuation including sequences of treatment, drug names and DoT, and reasons for end of treatment line.
- New nonserious AEs and SAEs assessed as related to cabozantinib (Adverse Drug Reactions (ADRs)) that start during the Post-Treatment Follow-up Period.
- Tumour assessment by the investigator (clinical and radiographic). If radiological assessment is performed, it should be indicated whether the assessment of progression is based on RECIST 1.1 or local standard of care. The most recent radiographic assessment performed before the visit is to be reported with the date and overall response. If clinical assessment is performed, the date of progression is to be provided if applicable.
- Concomitant medications for treatment of ADRs and changes to concomitant medications for treatment of pre-existing medical and surgical conditions (i.e. medical/ surgical history) at the time of occurrence of ADRs. Only AEs related to cabozantinib as assessed by the investigator will be collected, see above.
- Any further follow-up information for ongoing AEs (until resolution or stabilisation) and SS including pregnancy that occur during the Treatment Period.

If a participant is lost to follow-up during the Post-treatment Follow-up Period, multiple attempts should be made to contact the participant or designee, which should be documented in the participant's records.

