4.3 Study Data Collection

Participants will be treated in accordance with usual medical practice during their participation in this study. No additional assessments or tests will be required by this protocol. This study is non-interventional, thus if some assessments are not routinely performed by the investigator, they will not complete the corresponding sections in the eCRF.

Relevant data collected as part of routine medical care will be captured on an electronic Case Report Form (eCRF). These data will be transmitted to the sponsor for analysis. Data transmitted will be pseudonymized and will be identified by a participant number.

PROTOCOL FINAL V1.0: 30 JULY 2025

PAGE 20/52

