Abbreviations: AE=Adverse Event; CR=Complete Response; DCR=Disease control rate; ECOG=Eastern Cooperative Oncology Group; eCRF=electronic Case Report Form; EORTC=European Organisation for Research and Treatment of Cancer; EoS=End of Study; FU=Follow-Up; HrQoL=Health-related Quality of Life; NETs=Neuroendocrine tumours; PD=Progressive Disease; PR=Partial Response; PSP=Patient Support Program; QLQ-C30=Core Quality of Life Questionnaire; QLQ-GINET21= Quality of Life Questionnaire module for GI-NET patients; SD=Stable Disease; TA=Tumour Assessment.

IPSEN GROUP CONFIDENTIAL CONFIDENTIAL

PROTOCOL FINAL V1.0: 30 JULY 2025 PAGE 22/52

All data will be recorded as applicable and available during standard of care routine: if a specific diagnostic procedure is done according to clinical routine the corresponding data should be recorded in the eCRF, otherwise the corresponding part of the eCRF will be marked as not done.

- ^a EoS visit for participants still on cabozantinib treatment after 18 months.
- ^b Combined FU/EoS visit for participants who discontinued cabozantinib early (up to 15 months after Visit 1) and subsequent therapy switch.
- ^c Enrolment in the study is possible if cabozantinib treatment started up to 4 weeks prior to enrolment. See Section 4.1.
- ^d Clinical and/or TA via imaging to determine SD, PR, CR and PD. The type of assessment must be recorded in the eCRF.
- ^e The baseline radiological tumour assessment should be the most recent TA prior to enrolment.
- ^f In case of PD and cabozantinib treatment discontinuation and subsequent therapy switch, only the FU visit must be performed 3 months after end of cabozantinib treatment. Of note, cabozantinib treatment beyond progress is possible; in this case the participant is not passed over to the FU period but remains in the 18-month observation period. In addition, also other reasons e.g. drug intolerability or adverse events might lead to cabozantinib treatment discontinuation and switch to subsequent treatment; in these cases, also only the FU visit must be performed 3 months after end of cabozantinib treatment.
- g Including recording of dose modifications, overdoses, treatment interruptions and permanent study discontinuations along with the reason for discontinuation.
- h Performed if participant was enrolled up to 4 weeks after first dose of cabozantinib and Visit 1 was captured retrospectively. HrQoL baseline will then be taken.

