6.1.1 Primary Effectiveness Endpoint

Disease control rate (DCR):

DCR is defined as proportion of participants who within 6 months achieve complete response (CR), partial response (PR) or stable disease (SD) determined based on radiographic assessments between the date of the first dose of cabozantinib until the date of progressive disease (PD) or date of subsequent therapy.

Disease response definitions:		
CR	Complete response	Complete resolution of all visible disease.
PR	Partial response	Partial reduction in size of visible disease in some or all areas without any areas of increase in visible disease. Captures a decrease in disease volume even though disease is still present.
SD	Stable disease	No change in overall size of visible disease. Also includes cases where some lesions increased in size and some lesions decreased in size.
PD	Progressive disease	Increase in visible disease and/or presence of any new lesions. Includes cases where the clinician indicates PD or progression of disease as the overall assessment.

Table 6-1 Disease response definitions

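### The reference scan for DCR, ORR and PFS has no maximum age and no tie to first dose, so growth before cabozantinib can be scored as failure on it

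*Protocol*

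**What the plan says.** Section 4.5 names the scan that serves as baseline: "the most recent result of the tumour assessment at/before Visit 1 to obtain a baseline value required for determination of the primary endpoint, DCR". Footnote e of Table 4-1 (section 4.4) words it differently: "The baseline radiological tumour assessment should be the most recent TA prior to enrolment". At Visit 1 the eCRF takes its type and its date, listed as "Date of last imaging (reference images)", and the cabozantinib start date.

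No fresh scan can be asked for: "No additional assessments or tests will be required by this protocol" (section 4.3). On the routine interval, section 4.5 says "An assessment via imaging is expected approximately every 3 months as per standard of care". On timing of entry it says "Enrolment in the study is possible if cabozantinib treatment started up to 4 weeks prior to enrolment".

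Table 6-1 (section 6.1.1) defines PD as "Increase in visible disease and/or presence of any new lesions", with no size threshold. SD is "No change in overall size of visible disease", and a mixture of growing and shrinking lesions also counts as SD. Under section 8.4.3.1, SD, PR or CR at any post-baseline assessment is a success, but one reached only after PD does not count.

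**The concern.** By indication, every participant has progressed after an earlier systemic therapy (section 4.2), so a tumour may well grow between the reference scan and the first dose. If that gap is long, a tumour that stopped growing on the day treatment began can still look larger than its reference at the first on-treatment scan. The participant then has PD before any SD, PR or CR, and section 8.4.3.1 fixes that as a failure. ORR and PFS rest on the same tumour assessments.

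The anchor adds a second problem. Because it is enrolment and not first dose, a late-enrolled participant may have a reference scan taken on treatment. Change from that scan is not change since the start of cabozantinib.

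At stake is what the primary proportion means: part of it could reflect how recently routine imaging happened to be done.

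**Working it through.** **The plan's own precision figure.** Section 8.3: n = 150 × 0.9 = 135, expected DCR 145/198 = 73%. Half-width = 1.96 × √(0.73 × 0.27 / 135) = 0.0749, or 7.5 points. This agrees with the protocol and sets the scale.

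**Break-even count.** 10/135 = 7.4%. So about 10 participants who are controlled on drug but read as PD at the first scan would shift DCR by the whole half-width. If 2%, 5% or 10% of the 135 are so misread (about 3, 7 or 14 people), 73% becomes 71%, 68% or 63%.

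**An assumed model for the size.** The protocol gives neither scan ages nor growth rates, so both are assumptions here.
- Age of the reference scan at first dose: uniform from 0 to A months. A = 3 follows the expected imaging interval.
- Time to visible growth without cabozantinib: exponential with median m = 4, 6 or 12 months.
- Participants with SD have no shrinkage on drug.
- Share expected as SD: the trial cited in sections 2.3 and 8.3 gives ORR (0.19 × 64 + 0.05 × 134)/198 = 9.5%, about 10%; 73% − 10% = 63%.

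The fraction of stable participants misread is the mean of 1 − 0.5^(a/m) over a from 0 to A, that is 1 − [m/(A ln 2)] × (1 − 0.5^(A/m)). Multiplying by 63 gives the loss in DCR points.

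| Scan-age limit | m = 4 | m = 6 | m = 12 |
|---|---|---|---|
| A = 3 months: fraction misread | 0.220 | 0.155 | 0.082 |
| A = 3 months: DCR loss, points | 13.9 | 9.8 | 5.2 |
| 6 weeks (A = 1.38): DCR loss, points | 7.0 | 4.8 | 2.4 |
| 4 weeks (taken as A = 1): DCR loss, points | 5.2 | 3.5 | 1.8 |

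**How shrinkage on drug limits this.** With an assumed volume doubling time T in months and a scan 3 months old, diameter grows by 2^(3/(3T)) − 1 before first dose: 12%, 6% or 3% for T = 6, 12 or 24. Shrinkage on drug of about 11%, 6% or 3% cancels it. Participants who shrink by more than that are not misread, so the table leans high.

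**Size of a restricted set.** Under the same uniform ages, a 6-week limit keeps 1.38/3 = 46% of 135, about 62 participants. The half-width becomes 1.96 × √(0.73 × 0.27 / 62) = 11.1 points.

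**The case against.** The study is descriptive and may not require imaging, so the most recent routine scan is the only baseline available. The protocol leaves detailed analysis to a separate SAP, and both dates needed to derive the interval are already collected. Those facts shape the remedy. They do not remove the point, because the protocol itself fixes the reference scan, the PD definition and the rule that early PD is final.

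Three objections to the mechanism stand in part.
- Table 6-1 names no reference scan; that PD is judged against this baseline is inferred from section 4.5.
- Section 4.5 lets sites judge progression by RECIST 1.1 or local standard, so the rule that any increase is PD will not bind everywhere. Growth before first dose still counts in any comparison with the old scan.
- Mixed change is SD, and shrinkage on drug can offset earlier growth.

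On the anchor, Visit 1 is labelled Day 1 and treatment initiation and may be captured retrospectively. Section 4.5 could therefore be read as meaning a scan at or before first dose. Footnote e, which says enrolment, cannot.

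A reader might infer that the primary DCR is biased downward overall by 5 to 14 points, or that sites imaging just before treatment will look better. The documents support neither. Counting SD at any assessment and mixed change as SD both push DCR up, so the net direction is not established. The scan-age distribution is assumed, and patients who start after documented progression may have recent scans. Table 6-1 also sets no size threshold for PR, so the 63% SD share need not carry over. No comparison of DCR between sites is described.

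**Conclusion.** The point holds in limited form. The reference scan has no age limit and no stated tie to first dose, and the two passages that define it can pick different scans in participants enrolled after first dose. With an old scan, growth before treatment can become a final DCR failure, and this one mechanism acts downward.

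The size is unknown. The 5 to 14 points are an upper-end range resting on scan ages uniform over 3 months, assumed growth rates, no shrinkage on drug and a 63% SD share. The firmer statement is the break-even: about 10 of 135 misread participants match the stated 7.5-point half-width. The effect on ORR and PFS was not quantified, nor was that of an on-treatment reference scan. This is an inexpensive improvement to the plan and does not invalidate the primary analysis.

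**What to change.** 1. In section 4.5 and footnote e of Table 4-1, use one definition: the reference is the last scan on or before first dose, where one exists. Flag participants whose only available reference came after first dose.
2. In sections 8.4.3.1 and 8.4.3.2, or in the SAP, derive days from reference scan to first dose and report the distribution, with scans after first dose shown separately.
3. Pre-specify a sensitivity analysis of DCR, ORR and PFS restricted to reference scans within a fixed interval before first dose, shown beside the all-participant result. Fix the interval before the second interim analysis, which reports effectiveness, so that it is not chosen after seeing results.

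The interval could be 6 weeks or 4 weeks. Neither removes the problem: in the model above, 6 weeks still leaves about 7.0, 4.8 or 2.4 points, and 4 weeks about 5, 3.5 or 2. The shorter limit leaves less residual but fewer participants.

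Cost: some wording, one derived variable and one sensitivity table, with no extra scan or eCRF field. The restricted set is smaller (about 62 at 6 weeks under the assumed ages) and may be selected, since recently imaged patients can differ from the rest. It should support the main result and not replace it.

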8.4.3 Effectiveness Analysis

8.4.3.1 Primary Effectiveness Analysis

The primary endpoint is the DCR at 6 months, defined as the proportion of participants who, within 6 months achieve CR, PR or SD determined based on radiographic assessments between the date of the first dose of cabozantinib until the date of progressive disease (PD) or date of subsequent therapy.

The proportion of participants with DCR will be calculated by counting all participants who have SD, PR or CR at any post-baseline TA and dividing them by the number of participants in the FAS with at least one post-baseline TA. Participants who are treated with cabozantinib beyond progression but have not had SD, PR or CR prior to disease progression, will be considered to have no SD, PR or CR, even if they achieve SD, PR or CR after PD. DCR will be provided with the corresponding 95% CI.

In a secondary analysis, the DCR will be calculated similarly except that the count of participants who have SD, PR or CR at any post-baseline TA will be divided by the number of participants in the FAS.

PROTOCOL FINAL V1.0: 30 JULY 2025

PAGE 35/52

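### The one-visit-per-window and latest-scan-only rules can leave tumour assessments unrecorded, including an early PD scan on cabozantinib

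*Protocol*

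**What the plan says.** Four collection rules in the protocol act together.

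- **Visits.** Section 4.5, treatment period, where more than one visit falls in a 3-month window: "only the visit closest to the time point should be reported with most relevant information".
- **Scans.** Section 4.5, tumour assessment: "The most recent radiographic assessment performed before the visit is to be reported with the date and overall response". The list for the post-cabozantinib follow-up visit repeats this rule.
- **Slots.** Table 4-1 marks tumour assessment at Visit 1, at Visits 4 to 9 and at follow-up, but not at Visits 2 and 3. The text of Section 4.5 lists it for all of Visits 2 to 9.
- **After a switch.** Table 4-1, footnote f, on progression with stopping and a therapy switch: "only the FU visit must be performed 3 months after end of cabozantinib treatment".

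For regular visits, Section 4.5 also says that "the minimum information that must be recorded is the most recent result of the tumour assessment at/before Visit 1", which names the baseline assessment and none after it.

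Other text points the opposite way. Section 4.5 and the note under Table 4-1 ask for any assessment done in clinical routine to be entered in the eCRF. Section 4.5 adds "An assessment via imaging is expected approximately every 3 months as per standard of care" and "If clinical assessment is performed, the date of progression is to be provided if applicable".

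On the analysis side, Section 8.4.3.1 counts a participant as controlled on SD, PR or CR at any assessment after baseline and before PD, "dividing them by the number of participants in the FAS with at least one post-baseline TA". PFS (Sections 6.1.2 and 8.4.3.2) needs the date of radiological or clinical PD. Footnote j of Table 4-1 takes the final assessment preceding the switch as the baseline for next-line DCR.

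**The concern.** The analyses use the whole dated series of assessments up to PD, but the collection rules ask for one scan per reported visit. If two scans fall between reported visits, the earlier one has no place. The clearest case is a participant who progresses at Month 1 or 2 and switches. Table 4-1 has no slot at that point and footnote f asks only for the follow-up visit. There the latest scan may already be one on the next line.

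At stake are the primary DCR (both its numerator and its denominator), the PFS curve and landmarks, and the baseline for next-line DCR. A statistical analysis plan cannot restore a scan that was never entered.

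**Working it through.** **1. The protocol's own figure.** Section 8.3 gives n = 150 × 0.9 = 135 and an expected DCR of 73% (145/198). The half-width is 1.96 × √(0.73 × 0.27 / 135) = 7.49 points, which reproduces the stated ±7.5%.

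**2. When a scan is lost.** A scan made around an unreported visit is still captured, with its own date, at the next reported visit unless a newer scan replaces it. Loss therefore needs two or more scans between reported visits, or a PD scan followed by a next-line scan before follow-up.

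**3. DCR if a PD-only scan is lost.** Expected counts are 0.73 × 135 = 98.55 with disease control and 36.45 without. Treat the 36.45 as participants whose only scans show PD. If a share f of them lose that scan, they leave the denominator:

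DCR = 98.55 / (135 − 36.45f)

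- f = 5%: 98.55 / 133.18 = 74.0%
- f = 10%: 98.55 / 131.36 = 75.0%

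The supplementary DCR over the whole FAS does not change, because neither its numerator nor its denominator moves.

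**4. DCR if the only SD scan before PD is lost and the PD scan is kept.** If a share g of the controlled participants is affected, DCR = 98.55(1 − g) / 135:

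- g = 5%: 69.4%
- g = 10%: 65.7%

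Only participants with a single disease-control scan closely followed by PD can be affected, so these shares are illustrative. Per participant, the two errors are similar in size and opposite in sign. One lost PD-only scan gives 98.55/134 = 73.5%, up about 0.5 points. One lost SD scan lowers DCR by 1/135, about 0.7 points.

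**5. PFS.** Assume exponential PFS with the medians quoted in Section 2.3, and that a share f of PD events is lost and censored at that time. The hazard is multiplied by (1 − f), so the median becomes median / (1 − f).

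| PD events lost | epNET median (months) | pNET median (months) |
|---|---|---|
| 0% | 8.4 | 13.8 |
| 5% | 8.8 | 14.5 |
| 10% | 9.3 | 15.3 |

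At 5% lost, 12-month PFS moves from 37.1% to 39.0% (epNET) and from 54.7% to 56.4% (pNET).

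**6. How much loss is plausible.** A simulation applied the rules under these assumptions: exponential progression with the same medians, 3-monthly scans with random timing, a visit with each scan, ±1.5-month windows, and a 90% chance of a next-line scan before follow-up.

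| Timing SD (months) | Intervals with an extra scan | Scans lost | PD scans lost |
|---|---|---|---|
| 0.3 | 0% | 0% | 0% |
| 0.75 | 0% | about 4% | about 1% |
| 0.3 or 0.75 | 10% | 8–12% | 1–2% |
| 0.3 or 0.75 | 30% | 21–24% | 4–5% |

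Recorded DCR was 0 to 2 points lower than with all scans, because dropped SD scans outweighed dropped PD scans.

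**The case against.** The strongest reply is that the visit rule selects visits, not scans. Scans carry their own dates, imaging is expected about once per reporting slot, and the general instruction is to enter whatever was done. A PD result would plainly count as relevant information. Footnote f waives later regular visits; it does not say that the visit at which PD was found goes unreported. A stated minimum is not a limit. The stop date, the reason for stopping and a clinical progression date are collected, and clinical PD counts for PFS. The eCRF is not shown, so tumour assessment may already be a repeating form.

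Most of this stands, and it makes loss a possibility rather than a certainty. It does not remove the conflict: a site cannot follow both a general instruction to record everything and a specific one to report only the closest visit and the latest scan. The other fields help only in part. The cabozantinib regimen is not listed at follow-up, and a reason for stopping is not the radiographic assessment that DCR requires.

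A reader might infer that the rules inflate DCR by as much as the interval half-width. The documents do not support that. Reaching 0.73/(1 − 0.09) = 80.2% would need 9% of all participants to lose a PD-only scan, which is 9/27, one third of those without disease control. It would also ignore the lost SD scans that pull the other way. A reader might also infer that two of Visits 2, 3 and 4 must be dropped. The sentence before the window rule sets monthly visits to Month 3, so the window is more naturally read as the later 3-monthly phase. The wording should say so.

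**Conclusion.** The concern holds as a conflict between collection rules and analysis needs. The protocol permits post-baseline assessments, including an early PD scan on cabozantinib, to go unrecorded, and nowhere requires all scans up to PD or the first PD scan to be entered.

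The size cannot be derived from the protocol. With imaging strictly 3-monthly and on schedule the loss is near zero. Under the assumed loss of 5–10% of PD-only scans, the primary DCR rises by 1 to 2 points against a half-width of 7.5. Lost SD scans lower it, so the net direction is open. For PFS the direction is upward: about 0.4 months (epNET) or 0.7 months (pNET) if 5% of PD events are lost, given exponential PFS and censoring of the lost events. An individual PD date replaced by the next scan also moves later. The effect is modest, but the repair is cheap and has to be made at data collection.

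**What to change.** State in Section 4.5 that the one-visit-per-window and latest-scan rules do not apply to tumour assessments. Have sites enter every radiographic or clinical assessment done in routine care from first dose through first PD, and the last one before the next therapy starts. Each entry should carry its date, type, criterion (RECIST 1.1 or local standard) and overall response, whatever visit it falls near, and should be made at follow-up if still missing.

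Align Table 4-1 (Visits 2 and 3, footnote f), the minimum-information sentence and both tumour-assessment lists in Section 4.5 with this. Say that the 3-month window rule applies after Month 3.

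The cost is slightly more data entry and possibly an eCRF form change. No additional imaging is involved, so the study stays non-interventional.
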